1.1 Flowchart of Treatment Schedule

2 Introduction

This is non-invasive diagnostic study. It is easily achievable and simple to conduct. If proven to be a positive study, this may potential be a cost-effective method to detect cardiac arrhythmia.

2.1 Background

In the past few years, the use of smart phones and tablets with health-related applications has significantly proliferated. AliveCor ECG (figure 1) is an FDA-approved, CE-marked portable electrocardiogram (ECG) recorder that records a single channel (lead I) ECG rhythm strip using a compatible smart phone running a specific application.^{1,2} The recordings can be sent to a healthcare professional for interpretation. The healthcare professional accesses this information through the Provider Dashboard software.³

AliveCor Heart Monitor is an easy-to-use, highly-accessible, and cost-effective device which could be used to detect both paroxysmal and persistent arrhythmias in people who are asymptomatic as well as people with intermittent palpitations to determine the cause of their symptoms.

Figure 1

Description

The AliveCor Heart Monitor is a pocket-sized rectangular device containing 2 electrodes. It is either attached directly via an adhesive attachment plate to a mobile device or must be within 30 cm of the mobile device during operation. The AliveCor Heart Monitor can be removed from the plate when not in use, with the plate remaining attached to the mobile device. The mobile device must be a standard internet-enabled mobile phone or tablet, onto which the AliveECG app must be downloaded. The AliveCor Heart Monitor and AliveECG app are compatible with devices running Apple or Android operating systems.³

How to use it?

To record an ECG, the user places 2 or more fingers from the left hand onto 1 of the AliveCor Heart Monitor electrodes and 2 or more fingers from the right hand onto the other electrode. The user keeps contact with the electrodes for at least 30 seconds to ensure that a complete reading is taken, while keeping their arms still because arm movement may interfere with the ECG reading.

After the AliveCor Heart Monitor has taken a reading, it is sent wirelessly by a patented high frequency sound transmission to the mobile device, where it can be viewed using the AliveECG (Kardia) app. If or when the device has a suitable Wi-Fi or mobile connection, the recording will automatically synchronise with the secure encrypted AliveCor cloud server. The user can also send the recording directly to a relevant healthcare professional, such as a GP, to be read using the Provider Dashboard, which is a web-based application run from any standard PC.^{4,5} For this study, we will only use trust enabled devices such as iPod/iPad available in Cardiology department- Cardiac Investigation Unit (CIU).

Cost:

The AliveCor system consists of an AliveCor Heart Monitor and the Kardia app. The AliveCor Heart Monitor costs £62.49, excluding VAT, for a single unit. For orders of 50 units or more, the price reduces to £50 each, excluding VAT. The Kardia app is available as a free download from the Apple App Store or from Google Play, and the web-based Provider Dashboard is free to use. The estimated cost of a standard 12-lead ECG, in which a practice nurse applies the test and a GP reviews the results, to be £36.33 with the cost of an ambulatory ECG as £170 (NICE 2014).²

Evidence from literature

- To date, the device has been used in current practice to improve the detection of recurrent AF⁶ and to reliably monitor the QTc interval.⁷
- Lowres et al. (2014)⁵ conducted a community-based, opportunistic screening programme of 1000 people aged 65 years and over, using the AliveCor Heart Monitor to detect AF. The study was set in 10 pharmacies in Sydney, Australia. Following the analysis of 996 readings, excluding 4 people with pacemakers, the AliveECG app had 98.5% sensitivity (67/68; 95% CI 92.1%–100%) and 91.4% specificity (849/929; 95% CI 89.4–93.1%), using the cardiologists' diagnosis from the AliveCor Heart Monitor reading as the reference case.
- The REHEARSE-AF (Assessment of Remote Heart Rhythm Sampling Using the AliveCor Heart Monitor to Screen for Atrial Fibrillation) study is a randomized controlled trial of AF screening using an AliveCor Kardia monitor attached to a WiFi-enabled iPod to obtain ECGs (iECGs) in ambulatory patients. Patients \geq 65 years of age with a CHADS-VASc score \geq 2 free from AF were randomized to the iECG arm (500 individual) or routine care “RC” (501 individual). iECG participants acquired iECGs twice weekly over 12 months (plus additional iECGs if symptomatic) onto a secure study server with over read by an automated AF detection algorithm and by a cardiac physiologist and/ or consultant cardiologist. Time to diagnosis of AF was the primary outcome measure. The overall cost of the devices, ECG interpretation, and patient management were captured and used to generate the cost per AF diagnosis in iECG patients. Clinical events and patient attitudes/experience were also evaluated. Results showed that 19 patients in the iECG group were diagnosed with AF over the 12-month study period versus 5 in the RC arm (hazard ratio, 3.9; 95% confidence interval=1.4–10.4; $P=0.007$) at a cost per AF diagnosis of \$10 780 (£8255). There was a similar number of stroke/transient ischemic attack/systemic embolic events (6 versus 10, iECG versus RC; hazard ratio=0.61; 95% confidence interval=0.22–1.69; $P=0.34$). The study concluded that screening with twice-weekly single-lead iECG with remote interpretation in

ambulatory patients ≥ 65 years of age at increased risk of stroke is significantly more likely to identify incident AF than RC over a 12-month period.⁸

- The iPhone Helping Evaluate Atrial Fibrillation Rhythm Through Technology (iHEART)⁹ is an ongoing trial recruiting a total of 300 patients with a history of AF, with 150 patients receiving an iPhone with the mobile monitoring device and educational text messaging (the AliveCor system) and the remaining 150 patients continuing with their regular medical care. Each patient will be included in the intervention period for 6 months. The rate of recurrent AF and treatments meant to manage AF and other heart conditions will be determined for both groups. Patients in both groups will complete a series of questionnaires at the start and end of the 6-months study period to look at differences in quality of life and knowledge of AF.

Expected benefit:

The AliveCor Heart Monitor could be used in primary care as an alternative to other portable ECGs recorders to detect paroxysmal arrhythmias. There are several different portable ECGs available to the NHS. These devices, and the number of people in England who were monitored using these devices in 2013–14 following an outpatient appointment, are listed below (Health & Social Care Information Centre 2015):¹⁰

- ECG loop recorder – 63 people
- 24-hour ambulatory ECG – 80,264 people
- 48-hour ambulatory ECG – 2863 people
- Holter extended ECG – 7186 people
- Cardiomemo ECG monitor – 4973 people.

Given that the mean cost of ambulatory ECG monitoring is £170, the adoption of the AliveCor may produce savings to the NHS.

Why we are conducting this study?

There are no validated studies to evaluate its use in arrhythmias other than AF.

2.2 Study Objectives

Primary objectives: To assess the sensitivity and screening characteristics of AliveCor recording to detect a wide range of cardiac arrhythmias (AF, atrial flutter, SVT, VT, paced rhythm and pre-excitation) by 4 different readers.

Secondary Objectives:

- To test whether the AliveCor device will be non-inferior to the 12 lead ECG with respect to diagnosis of the arrhythmia when read by a Consultant Electrophysiologist.
- To compare the screening characteristics of the AliveCor's automated diagnostic algorithm with its screening characteristics when read by a Consultant Electrophysiologist, a general Consultant Cardiologist and a General Practitioner.

3 Study Design

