Methodology / Design	
Non-randomised open label diagnostic study
 
We are planning to record 250 pre-defined abnormal ECGs (50 each of atrial fibrillation, atrial flutter, pre-excitation, ventricular tachycardia, , supraventricular tachycardia) and 150 control ECGs (100 sinus rhythm, 50 sinus tachycardia) using both the AliveCor Smartphone device and a 12-lead ECG. All 400 ECGs will then be read by 3 blinded reporters – a Consultant Electrophysiologist, a Consultant General Cardiologist and a General Practitioner. The output of the AliveCor automatic detection algorithm will also be recorded as a fourth reporter. The screening characteristics of all 4 reporters using the AliveCor device vs the definitive 12 lead ECG will be analysed and compared.
 
Patients can be recruited from different cardiology clinics; at the end of an exercise test to record sinus tachycardia, and in the catheter lab during electrophysiological studies/ ablation procedures to record arrhythmias.
 
Every patient will be counselled about the project by a member of the cardiology / research team (doctor or qualified research nurse) and will be provided with a patient information sheet. Patients will be given up to 2 weeks to consider participation in the study. If in agreement, written informed consent will be obtained.
 
A 30-second ECG tracing will be obtained by simply holding the Smartphone and placing at least 1 finger from each hand on electrodes embedded into the back of the Smartphone case (figure 2). For sedated patients in the catheter lab, AliveCor electrodes will be placed and taped on patient chest wall, left parasternal third intercostal space. The AliveCor ECG tracing will be recorded as close to simultaneously as the 12 lead ECG

	recording as possible.
Duration	2 years
Participating Centres	Blackpool Victoria Hospital
Primary End Point	Screening characteristics and diagnostic accuracy of AliveCor ECG recordings to detect cardiac arrhythmias
Number of participants	400
Main Inclusion /Exclusion Criteria	
Inclusion:
 
 • Male or female patients >18 years with 12 lead ECG finding of arrhythmia, manifest pre-excitation, pacing rhythm, sinus rhythm or sinus tachycardia. 
Exclusion Criteria:
 
 • Patients <18 years of age. • Patients unable to or unwilling to use the device.

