Statistical Methodology and Analysis	
400 patients are planned to be recruited as follows:
 
50 patients with supraventricular tachycardia (SVT) 50 patients with atrial flutter (AFl) 50 patients with atrial fibrillation (AF) 50 patients with ventricular tachycardia (VT) 50 patients with manifest pre-excitation 50 patients with sinus tachycardia to constitute the tachycardia control group
 
100 normal ECGs will also be collected from the first 100 patients who have regular sinus rhythm to constitute the sinus rhythm control group.
 
ECGs will be recorded in duplicate, with one recording being made using the AliveCor device, and one recording being made using a normal 12-lead ECG. Recordings will be undertaken as close to simultaneously as possible. The ECG diagnosis will be made by the lead Electrophysiologist on the 12-lead ECG so produced and this will be taken as the correct ECG diagnosis.
 
All ECGs (both 12-lead and AliveCor) will be reported by a Consultant Electrophysiologist, a General Cardiologist and a General Practitioner, blinded to the full study protocol and the patient allocation group. The output of the AliveCor algorithm for automatic ECG diagnosis will also be recorded. The readers will firstly read the AliveCor ECGs and at a later date read the 12-lead ECGs to prevent comparisons between the ECGs and to give accurate screening characteristics for AliveCor ECGs.
 
The diagnostic accuracy and screening characteristics of ECGs generated by the AliveCor device will be reported for each arrhythmia individually and in combination both by each reporter. To calculate screening characteristics, ECGs of sinus rhythm and sinus tachycardia will also be included in each analysis as normal controls. 95% confidence intervals will be calculated.
 
The primary end-point will be the sensitivity and screening characteristics of detecting each arrhythmia individually and in combination by each reporter using the AliveCor device, calculating 95% confidence intervals.
 
The binomial exact calculation would be used to calculate confidence intervals.
 
With a sample size of 50 patients with one arrhythmia, a sensitivity of 80% would produce a 95% confidence interval of 68.9% to 91.1%. With a sample size of 250 (all arrhythmias combined), a sensitivity of 70% would produce a 95% confidence interval of 64.5% to 75.1%, i.e. an absolute error of $\pm 5\%$.
 
The main secondary end-point will be to compare the sensitivity of a

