4.1.2 Exclusion Criteria

1	Patients <18 years of age.
2	Patients unable to or unwilling to use the device.
3	Patients with cardiac pacemaker, ICDs, or other implanted electronic devices

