6.1 Sample Size Determination

With a sample size of 50 patients with one arrhythmia, a sensitivity of 80% would produce a 95% confidence interval of 68.9% to 91.1%. With a sample size of 250 (all arrhythmias combined), a sensitivity of 70% would produce a 95% confidence interval of 64.5% to 75.1%, i.e. an absolute error of $\pm 5\%$.

The main secondary end-point will be to compare the sensitivity of a Consultant Electrophysiologist in detecting all arrhythmias using the AliveCor device *vs* the originally coded 12-lead ECG, to test whether the AliveCor device is non-inferior to the original 12-lead ECG diagnosis. Assuming a 95% one-sided confidence interval and a power of 80%, if there is a true difference in sensitivity in favour of the 12-lead ECG over an AliveCor ECG of 10%, and then a sample size of 301 arrhythmias would be needed to exclude a difference in favour of the 12-lead ECG of more than 16%.

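### Paced rhythm is in the primary objective but has none of the 400 planned ECGs, the summary and body differ on patients with implanted devices, and the combined precision figure fits 300 arrhythmias, not 250

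*Combined protocol and SAP*

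**What the plan says.** **Objective.** The primary objective in section 2.2 covers "a wide range of cardiac arrhythmias (AF, atrial flutter, SVT, VT, paced rhythm and pre-excitation) by 4 different readers". That is six target rhythms, one of them paced.

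**Recruitment.** The Methodology / Design entry of the Study Summary states "We are planning to record 250 pre-defined abnormal ECGs", at 50 each for AF, atrial flutter, pre-excitation, VT and SVT, with 150 controls. The Statistical Methodology and Analysis entry says "400 patients are planned to be recruited as follows" and gives the same five arrhythmia groups, 50 patients with sinus tachycardia and 100 in sinus rhythm. Neither list has a paced group.

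**Eligibility.** The summary's inclusion line reads "12 lead ECG finding of arrhythmia, manifest pre-excitation, pacing rhythm, sinus rhythm or sinus tachycardia", and its exclusions do not mention devices. Section 4.1.2 excludes "Patients with cardiac pacemaker, ICDs, or other implanted electronic devices". Section 4.1.1 does not name pacing, but it does not name sinus tachycardia either.

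**Precision.** On method, the summary says "The binomial exact calculation would be used to calculate confidence intervals", and section 6.2 says the same. Section 6.1 states "With a sample size of 250 (all arrhythmias combined), a sensitivity of 70% would produce a 95% confidence interval of 64.5% to 75.1"%, which it describes as an absolute error of ±5%. The same section says that "a sample size of 301 arrhythmias would be needed to exclude a difference in favour of the 12-lead ECG of more than 16"%.

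**The concern.** The plan promises sensitivity with a 95% confidence interval for each arrhythmia separately and for all combined. With no paced ECG planned, there is nothing from which to estimate the paced-rhythm figure, and no analysis method can supply it. A report written against section 2.2 would have one of its six named rhythms without data.

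The eligibility lists add an operational problem. Recruitment takes place partly in cardiology clinics. For a clinic patient paced by an implanted device, someone working from the summary would enrol and someone working from section 4.1.2 would not.

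The precision statement belongs with this point because it may be affected by the same thing. If the words on paced rhythm were simply deleted, the stated interval would still be too narrow for the 250 arrhythmias that will be recruited.

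**Working it through.** **1. Are all 400 places allocated?** Inputs: the group sizes in the Study Summary, Statistical Methodology and Analysis.

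- Arrhythmias: SVT 50 + atrial flutter 50 + AF 50 + VT 50 + pre-excitation 50 = 250.
- Controls: sinus tachycardia 50 + sinus rhythm 100 = 150.
- Total: 250 + 150 = 400, which reproduces the plan's total.
- Places left for paced rhythm: 400 − 400 = 0.

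**2. Do the eligibility texts agree?**

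| Patient | Study Summary | Section 4.1.2 |
|---|---|---|
| Paced by an implanted device | Admitted (pacing rhythm listed, no device exclusion) | Excluded |
| Paced without an implanted device | Admitted | Not excluded |

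The texts differ only in the first row. The second row is open in both, but no group is planned for it. Section 4.1.1 is not counted as a conflict: it admits any arrhythmia and also omits sinus tachycardia, which is certainly to be recruited, so its silence on pacing proves little.

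**3. Does the combined interval follow from n = 250?** Inputs: sensitivity 70%, n = 250 and the exact binomial method (sections 6.1 and 6.2). With x events in n, the exact (Clopper-Pearson) 95% limits are:

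- lower = 2.5% quantile of Beta(x, n − x + 1)
- upper = 97.5% quantile of Beta(x + 1, n − x)

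| Method | x/n | 95% interval |
|---|---|---|
| Printed in the plan | 70% of 250 | 64.5% to 75.1% |
| Exact | 175/250 | 63.9% to 75.6% |
| Normal approximation | 175/250 | 64.3% to 75.7% |
| Wilson | 175/250 | 64.1% to 75.3% |
| Exact | 210/300 | 64.5% to 75.1% |

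None of the three methods at n = 250 gives the printed limits. The exact method at n = 300 gives 64.47% to 75.13%, which rounds to them.

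- Width printed: 75.1 − 64.5 = 10.6 points.
- Width at n = 250: 75.6 − 63.9 = 11.7 points.
- Error around 70% at n = 250: 70 − 63.9 = 6.1 below and 75.6 − 70 = 5.6 above, against the stated ±5%.

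Six groups of 50 would make 300. That fits an earlier sixth group, but the documents do not say there was one, so this is inference only.

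**4. How do these totals compare with the non-inferiority requirement?**

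- Five groups: 301 − 250 = 51 short.
- Five groups plus a paced group of assumed size 50: 250 + 50 = 300, so 301 − 300 = 1 short. Total enrolment would be 400 + 50 = 450, a rise of 50/400 = 12.5%.

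**The case against.** The strongest reply is that inclusion and exclusion criteria are read together. The summary's list is headed as the main criteria, so it is openly abridged, and section 4.1.2 excludes devices, not a paced rhythm as such. Pacing in the catheter lab during an electrophysiological study would satisfy both texts. This is right as far as it goes: the texts do not contradict each other on pacing in general. What stands is narrower. A reader of the summary alone would miss the device exclusion, so the two texts give different answers for a patient paced by an implanted device. The reply also does nothing for the objective, since all 400 places are taken by other rhythms.

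A second reply is that little turns on this. The primary endpoint wording in section 3.2 and the methods in section 6.2 do not name paced rhythm, and deleting it from section 2.2 would change no planned analysis and bias no estimate. That is fair, and it limits the weight of the point. It does not remove a component of the primary objective that has no data planned for it.

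A third reply is that the interval and the shortfall against 301 would exist even if pacing had never been mentioned. That is also fair: the link to a sixth group is inference. The interval is still wrong for n = 250, and deleting the words on pacing would not correct it. The per-arrhythmia interval in the same paragraph is a separate error. The printed 68.9% to 91.1% for 80% of 50 is the normal approximation, whereas the exact interval for 40/50 is 66.3% to 90.0%.

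**Conclusion.** The concern holds. Paced rhythm is 1 of 6 rhythms in the primary objective and has 0 of 400 planned places, so that part of the objective cannot be answered as planned. The summary and section 4.1.2 disagree on patients paced by an implanted device. The combined 95% interval at 70% sensitivity is 11.7 points wide for the 250 planned arrhythmias, not the printed 10.6.

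The allocation result rests only on the plan's own group sizes. The interval result rests on the plan's 70% sensitivity and its stated exact method. The idea of a dropped sixth group is not needed for either. The plan should be corrected, but the damage is contained: the other five rhythms can be reported as intended.

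**What to change.** If enrolment stays at 400:

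1. In section 2.2, limit the primary objective to the five recruited rhythms: AF, atrial flutter, SVT, VT and pre-excitation, with a combined n of 250.
2. Make the summary criteria and sections 4.1.1 and 4.1.2 agree on pacing and implanted devices. Which rule applies is for the sponsor to decide.
3. In the Study Summary and section 6.1, restate the combined precision by the exact method: at 70% sensitivity and n = 250, 63.9% to 75.6%, about −6.1 to +5.6 points in place of ±5%. Correct the n = 50 interval at the same time, so that the paragraph uses one method throughout.
4. State that 250 arrhythmias is 51 below the 301 given for the non-inferiority comparison. Narrowing the objective does not close that gap, and it needs its own decision.

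The cost is a text amendment with no change in patient numbers. The plan gives up any claim about paced rhythm and states a wider interval.

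The alternative is to keep paced rhythm and plan a group for it. At an assumed size of 50, enrolment rises from 400 to 450 (+12.5%) and the combined set to 300. The printed combined interval would then be correct, although its stated n would have to change, and the set would be 1 short of 301. The eligibility texts would still have to be reconciled.

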3.1.1 General

Open label non-randomised diagnostic study. Readers will be blinded to the ECG diagnosis.

Expected study duration: 2 years

3.1.2 Study procedure

Every patient will be counselled about the project by a member of the Cardiology / Cardiology research team (doctor or qualified research nurse) and will be provided with a patient information sheet. Patients will be given up to 2 weeks to consider participation in the study. If in agreement, written informed consent will be obtained.

A 30-second ECG tracing will be obtained by simply holding the Smartphone and placing at least 1 finger from each hand on electrodes embedded into the back of the Smartphone case (figure 2). For sedated patients in the cath lab, AliveCor electrodes will be placed and taped on patient chest wall, left parasternal third intercostal space. A 12-lead ECG will also be recorded as near to simultaneously as possible. The 12-lead ECG will be reviewed by Principal Investigator (PI) to ensure that the ECG rhythm has not changed.

3.2 Primary Study Endpoints

Sensitivity and screening characteristics of AliveCor recording to detect cardiac arrhythmias.

3.3 Secondary Study Endpoints

To test whether AliveCor is non-inferior to the 12-lead ECG.

To compare the screening characteristics of the automated AliveCor algorithm to that of a Consultant Electrophysiologist, general Consultant Cardiologist and General Practitioner.

